PROTOCOL FOR RESEARCH INVOLVING HUMAN SUBJECTS

**TITLE OF PROJECT: Cervical Spondylotic Myelopathy Surgical Trial (CSM-S Trial)
VERSION: 6.0, DATE: 12-17-24**

Study Sponsor: Patient-Centered Outcomes Research Institute (PCORI) & Alan and Jackie Stuart Spine Research Center

	Name	Signature	Email Address
Principal Investigator:	[name] MD		[contact]
Other Investigator(s):			
Correspondent			

Mailing Address:

[name]
[name]

[contact]
[contact]

II. DESCRIPTION OF STUDY

A. Purpose

1a. To determine if ventral surgery is associated with superior SF-36 PCS outcome at one year follow-up compared to dorsal (fusion or laminoplasty) surgery.

1b. To determine if, compared to pre-operative baseline status, both ventral and dorsal surgery for CSM improve symptoms of spinal cord dysfunction using mJOA.

2. To determine if, from a patient perspective, health resource utilization (out-of-pocket expenses and loss of productivity) for ventral surgery, dorsal fusion, and laminoplasty surgery are different.

3. To determine if cervical sagittal balance post-operatively is a significant predictor of SF-36 PCS outcome.

B. Background

Surgical decompression for CSM can improve its disabling symptoms, but surgical complications are common and many of these complications affect patients' overall health-related quality of life. The optimal surgical treatment, therefore, remains controversial, with disagreement between three main approaches: ventral decompression and fusion, dorsal decompression and fusion, or dorsal laminoplasty. This study aims to test the hypothesis that ventral surgery is associated with superior SF-36 PCS outcome at one year follow-up compared to dorsal approaches and that both ventral and dorsal surgery improve symptoms of spinal cord dysfunction using the mJOA score. A secondary hypothesis is that health resource utilization for ventral surgery, dorsal fusion, and laminoplasty surgery are different. A third hypothesis is that cervical sagittal balance post-operatively is a significant predictor of SF-36 PCS outcome.

C. Specific Location of Study

This is a multi-center trial. Subjects will be entered into the study from 10 separate centers.

D. Probable Duration of Project

Subjects will be recruited into the study over an 18 month period. All subjects will be followed for 5 years with clinical questionnaires.

E. Research Plan

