The sample size will be inflated by 5% to accommodate multiple significance testing using an O'Brien-Fleming stopping boundary. Based on our preliminary data and pilot studies, withdrawal and loss-to-follow-up are not expected to be high. The sample size will be further inflated by 10% to accommodate attrition during the follow-up. Thus, 159 total patients will be recruited and randomized. **Ten high volume surgeons/ centers with the necessary expertise to permit patient randomization (16 randomized CSM cases/ site) have been selected to achieve the goal of enrolling 159 randomized patients over 18 months. An additional 91 nonrandomized patients will be enrolled into the study.**

Sample size for Specific Aim #1b (Compared to pre-operative baseline status, both ventral and dorsal surgery for CSM improve symptoms of spinal cord dysfunction at one year follow-up):

Using the sample size estimate for Specific Aim #1a and assuming ~10% attrition during follow-up, we expect to have 55 ventral surgery and 82 dorsal surgery patients (total = 137 patients) available for analysis. We will be able to detect changes from baseline pre-operative mJOA status as small as 2.0 points (clinically important difference) for both the ventral surgery cohort and the dorsal surgery cohorts at one year. Assumptions for this sample size analysis include Type I alpha = 0.025, power at 90%, and range of within-subject correlation of 0.60 to 0.70.

H. Economic Considerations

No subject will incur any additional cost for participating in this study. All of the pre- and post-operative CT, MRI, flexion-extension x-rays, and pre-operative sagittal balance films are considered standard of care. The post-operative sagittal balance films, which only randomized patients will receive, are not considered standard of care and will be billed directly to the research fund. All costs associated with the administration of the study will be assumed by the Patient-Centered Outcomes Research Institute (PCORI) and/or the Lahey Comparative Effectiveness Research Institute.

[figure not shown]
III. HUMAN SUBJECTS

A. Subject Population, Recruitment

Eligibility Criteria: Patients aged 45-80 years with CSM (≥ 2 levels of spinal cord compression from C3 to C7) presenting with ≥ 2 of the following symptoms/signs: clumsy hands, gait disturbance, hyperreflexia, up going toes, bladder dysfunction.

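### The Aim 1b power paragraph counts 137 evaluable patients where its own attrition gives about 143, and uses an unexplained alpha of 0.025 with an apparently per-cohort 90% for a claim about both approaches

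*Combined protocol and SAP*

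**What the plan says.** Section II.A, item 1b, sets the aim of determining whether, relative to baseline, "both ventral and dorsal surgery for CSM improve symptoms of spinal cord dysfunction using mJOA". The Aim 1b heading in II.G.d repeats the word both.

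The sample-size text for Aim 1a takes a fixed-design total of 137 (55 ventral, 82 dorsal; last row of the table). It adds 5% for an O'Brien-Fleming boundary and a further 10% for attrition, and concludes: "Thus, 159 total patients will be recruited and randomized".

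The Aim 1b paragraph then says that, "assuming ~10% attrition during follow-up, we expect to have 55 ventral surgery and 82 dorsal surgery patients", 137 in total. It describes the smallest effect that the trial can pick up as "changes from baseline pre-operative mJOA status as small as 2.0 points (clinically important difference) for both the ventral surgery cohort and the dorsal surgery cohorts". The assumptions listed are "Type I alpha = 0.025, power at 90" per cent and a "range of within-subject correlation of 0.60 to 0.70".

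The paragraph gives no SD for mJOA, no side for the 0.025, no reason for choosing it, and no statement of whether 90% refers to each cohort or to both together. II.G.c gives no success rule for Aim 1b.

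**The concern.** The evaluable number does not follow from the inputs beside it. The plan inflates 137 twice to reach 159, then removes one of the two inflations and reports that it is back at 137.

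The alpha and power do not clearly match the claim either. If the aim is met only when both within-cohort tests show improvement, testing each at two-sided 0.05 already protects the claim. Halving alpha for two tests protects a different claim, that at least one approach improves. A power of 90% in one cohort is also not the probability that both tests succeed. At stake are a power statement that a reader cannot check and, on one reading of 0.025, a few points of power given up for error control that the claim does not need.

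**Working it through.** **1. Evaluable number (inputs all from II.G.d).**

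- The plan's 159: 137 × 1.05 = 143.85, and 143.85 × 1.10 = 158.2, rounded up to 159. This reproduces.
- After 10% attrition: 159 × 0.90 = 143.1. At 2:3 allocation, 143 × 0.4 = 57.2 and 143 × 0.6 = 85.8, so about 57/86.
- Undoing the 10% inflation by division instead: 159 / 1.10 = 144.5. This does not give 137 either.
- Loss implied by 137: 1 − 137/159 = 13.8%.
- Randomised number for which 10% loss leaves 137: 137 / 0.90 = 152.2, not 159. The gap is the 5% interim inflation.

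**2. Error rate of a both-must-succeed claim.** A false claim means that at least one cohort does not truly improve. The probability that both tests are significant cannot exceed the probability that the test in that cohort is significant. With each test at two-sided 0.05 (2.5% in the direction of improvement), the joint claim is therefore held at that same level without a split.

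**3. Power.** The plan's 90% cannot be reproduced, because no mJOA SD is given. I therefore assumed that 2.0 points is the change at which the smaller cohort (n = 55) has exactly 90% power, with paired t-tests, a common SD of change and independent cohorts. Joint power is the product of the two cohort powers.

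If 0.025 is two-sided, the implied standardised change is 0.486, so the SD of change is 2.0/0.486 = 4.11. From SD of change = SD × √(2(1 − ρ)), the raw SD is about 4.6 at ρ = 0.60 and 5.3 at ρ = 0.70.

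| Evaluable | Alpha per cohort | Ventral | Dorsal | Both |
|---|---|---|---|---|
| 55/82 | 0.025 two-sided | 90.0% | 98.2% | 88.4% |
| 55/82 | 0.05 two-sided | 94.3% | 99.2% | 93.5% |
| 57/86 | 0.025 two-sided | 91.1% | 98.6% | 89.9% |
| 57/86 | 0.05 two-sided | 95.0% | 99.4% | 94.5% |

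The gain at 55/82 is 5.2 points before rounding.

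If 0.025 is one-sided, it is the same test in the direction of improvement as two-sided 0.05. Calibrated to 90% in the ventral cohort, the dorsal cohort has 97.8% and both together 88.1%. Changing the stated alpha then gains nothing.

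**4. Sensitivity to the correlation.** Suppose the two-sided 90% holds at ρ = 0.60, the unfavourable end of the plan's range, and the SD stays fixed. At 55/82 the gain is 5.2 points at ρ = 0.60, 3.4 at 0.65 and 1.9 at 0.70.

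**5. Sensitivity to the SD.** The raw SDs below are assumptions. Power is by normal approximation, Φ(2.0√n / SD of change − z), which runs slightly above the t-test, at 55/82 and ρ = 0.60.

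| Assumed raw SD | Both, 0.025 two-sided | Both, 0.05 two-sided |
|---|---|---|
| 3 | 99.95% | 99.98% |
| 4 | 96.9% | 98.5% |
| 4.5 | 91.5% | 95.2% |
| 5 | 82.9% | 89.6% |

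Over these SDs the cost of a two-sided 0.025 runs from about 0 to about 7 points.

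**The case against.** The plan never says that alpha is split. The aim is directional, and a one-sided 0.025 would be a conventional choice that costs nothing. The return-to-work plan (II.G.c) also uses 0.025, but there it says openly that this accounts for two comparisons, and those are pairwise comparisons of as-treated groups. That makes a split in Aim 1b plausible, not documented. This stands, and it is why the power loss can only be conditional.

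The per-cohort reading of 90% is likewise an inference. Even at the exact-90% calibration the joint figure is only 1.6 points lower, and over much of the stated correlation range it could exceed 90%. This also stands.

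Using 137 is conservative for Aim 1b, so no conclusion there is harmed. That is right about direction, but the text says that 137 is expected after about 10% attrition and does not offer it as a deliberate lower bound. A loss of 13.8% is not about 10%.

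A reader might also infer that, if 137 is the true expectation, the primary aim falls below 90% power because the interim inflation is not delivered. The documents do not support a figure for this. They say that 137 gives at least 90%, not exactly 90%, and they do not give the number of looks that sets the inflation needed. On that row's printed inputs (difference 5, SD 10, ρ = 0.70, 2:3), the usual ANCOVA formula gives (1.960 + 1.282)² × 100 × (1 − 0.49) / (25 × 0.24) ≈ 89 patients for 90% power, so 137 does not pin power at 90%.

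**Conclusion.** The mismatch in the evaluable number is firm and needs no assumption: 10% attrition from 159 leaves about 143 (57/86), not 137 (55/82). It understates Aim 1b power slightly.

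It is also firm that a claim about both approaches needs no alpha split, and that the stated 90% cannot be checked without the mJOA SD, the side of the test and the definition of power.

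The loss of power is conditional. It is about 5 points (93.5% against 88.4%) if 0.025 is two-sided and the ventral cohort has exactly 90% at 2.0 points. It is less with a smaller SD, a higher correlation or a larger true change, and zero if 0.025 is one-sided. A reader might infer that the plan does split alpha and does lose 5 points. The documents establish neither.

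Importance is low: II.G.b lists mJOA change as a secondary endpoint, although Aim 1b is part of the first aim and has its own power statement.

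**What to change.** In the Aim 1b paragraph of II.G.d, with the rule repeated in II.G.c:

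- Replace 137 (55/82) by 143 (57/86), or keep 137 and state that it assumes 13.8% loss.
- State that Aim 1b is met only if both within-cohort tests show significant improvement, each at two-sided 0.05 (equivalently one-sided 0.025), with no split.
- State the mJOA SD assumed and its source, and report the joint power that follows from it over the 0.60 to 0.70 correlation range. The joint powers shown above should not be copied into the plan, because they rest on an SD back-calculated from the 90%.

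The cost is a few sentences, with no extra patients or data. The one downside is that a claim of improvement for a single approach would then need its own multiplicity rule. Aim 1b as worded makes no such claim.

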Appendix I: Study Schema
